**f. Definition of treatment failure or participant removal criteria.**

Participants will be discontinued from the study if they (1) ask to be removed from the study (2) are found to be using other smoking cessation treatments (3) develop a medical condition precluding the use of the iCO monitor such as COPD (4) develop a serious adverse event (SAE).

**g. Description of what happens to participants receiving therapy when study ends or if a participant's participation in the study ends prematurely.**

The participant will continue to receive care at these facilities should he/she choose to leave the study for any reason. If a participant leaves the study prematurely due to an adverse event, text messages will stop being sent to them.

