### **c. Statistical plan including sample size justification and interim data analysis.**

#### **Data analysis plan**

**Overview** The primary outcome measure for the RCT is proportion of participants with biochemically verified smoking cessation as of 1-month; the primary exposure is study arm, brief-advice only vs. COach2Quit. We will compare proportions of smoking abstinence between study arms at 1-month.

Covariates of interest (e.g. sex, age, race, ethnicity, education, income, smoking history) will be assessed for relationship to prevalence of quitting. These comparisons will utilize the chi-square test for categorical variables and either the Student's t-test or the Wilcoxon signed rank test for continuous variables. Multivariate logistic models will be generated using forwards stepwise model selection, including study arm and all variables with  $p < 0.2$  or odds ratio  $< 0.5$  or  $> 2.0$  at the univariate level, ultimately generating the most parsimonious model.

We will conduct intent-to-treat analyses, providing the purest analysis for an RCT. For these analyses, participants who are lost to follow-up will be considered smokers from the date of last contact. This approach is conservative, as it will likely include participants who have not received either study intervention, but point estimates will be biased towards the null. This approach has been widely adopted in smoking cessation studies. We will compare rates of losses to follow up across the study arms, and look for differences in characteristics of those lost between the arms.

We will analyze number of smoke-free days obtained from questionnaires by comparing the proportions of smoke-free days between arms with a Wilcoxon signed rank test. We will estimate either the absolute difference in proportions, or after a  $\log(\text{days smoke-free}+1/\text{total days of follow up})$  transform if appropriate, with 95% confidence intervals. We will also measure durability of treatment effects using consecutive visits with biochemically verified smoking cessation.

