### **Sample Size**

Dated: 15 May 2017

This is a pilot RCT, thus our sample size is not powered to find significant differences between arms, but will provide estimates for future larger studies. We anticipate cessation rates of 20% in the COach2Quit arm and 10% in the brief-advice only arm at 1-month. We will enroll 150 participants into the study over 4 months, randomized 1:1.

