#### **8. Risks**

##### **a. Medical risks, listing all procedures, their major and minor risks and expected frequency.**

Participation in this trial poses **minimal risk** to the participant's health.

There are no known medical contraindications for use of the exhaled breath CO machines for healthy individuals. These criteria are consistent with our previous research and have posed no undue risk or adverse events to participants.

Study procedures are anticipated to be associated with **minimal medical risk**, but if a participant develops any side effects, they will be referred for immediate care. A safety protocol will be written and closely adhered to for participants who experience serious adverse events.

Although privacy and confidentiality will be ensured throughout all study procedures, some questions may make the participant uncomfortable, such as questions about personal tobacco use or education. Should any breach in confidentiality occur, details of the breach will be fully investigated and documented and reported to the Johns Hopkins University IRB within seven days.

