##### **b. Steps taken to minimize the risks.**

Risks to confidentiality will be minimized by the following procedures: participant interviews will be conducted in a private area of the clinic, study records will be stored in locked cabinets in secure locations, study records will be accessible only to authorized study staff, databases will be password-protected and accessible only to authorized study staff. Study records and databases will not be accessible by employers, and study participation will not affect employment status. All study personnel will complete a course in research subjects' protection. Protected Health Information (PHI) that will be collected from participants are name, age, and phone number. All PHI will be stored on paper, not electronically, in a locked cabinet in a secure location, and PHI will only be accessible to authorized study staff. **No PHI will be collected or stored online or within the smartphone application.** All participants will receive a unique user ID that will be used in the smartphone application. This ID will be linked to their PHI that will be recorded on paper and stored securely. The PHI will be owned by the Principal Investigator, [name], at JHU.

A detailed protocol will be established for all research staff to be trained to identify an Adverse Event (AE) or Serious Adverse Event (SAE) and to follow in the event of an AE or SAE. The research staff person identifying an AE or SAE will immediately report the event to [name]. The study staff will discuss the situation with [name], and submit the appropriate paperwork to the IRB within 24 hours of becoming aware of the event. These events will also be documented during the IRB's yearly continuation review of the project.

Dated: 15 May 2017

This study will use the NIDA's Common Adverse Events (AEs) and Serious Adverse Events (SAEs) definitions for clinical research. Adverse events are defined as any event or outcome that has resulted in harm to the participant, has affected the participant detrimentally, has worsened as a result of participation in the study, or that has resulted in increased risk to the participant or others whether or not the risk actually results in harm. Specific SAEs include:

- death;
- serious injury;
- a life-threatening experience;
- hospitalization;
- a persistent or significant disability or capacity;
- suicidal ideation/attempts;

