In addition, all reactions to the study device that are not considered an SAE will be documented as an AE. The PI will be available by phone for any study issues.

Any AE that occurs between the time a participant signs the informed consent form and the time he or she departs the study at the end of the final follow-up visit will be captured and recorded. In the event that the participant is withdrawn from the study due to an AE, it will be recorded on the case report forms as such. The participant will be followed and treated by the Investigator until the abnormal parameter or symptom has resolved or stabilized. It is up to the clinician to determine that the SAE is either resolved, or that it has reached a stable state, after which no further follow-up is necessary. There will be documentation to support that determination.

Once an AE or SAE is known, research team members at the study site should ensure that participants receive appropriate care. All actions taken by the study staff after observing an AE or SAE should be documented, including increased monitoring of the participant, suspension of the treatment, etc.

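### Section 4f takes any participant with an SAE out of the study, not just off the app or monitor, and so appears to end 1-month outcome collection for people who could still attend

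*Combined protocol and SAP*

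**What the plan says.** Section 4f lists four grounds for removal under the opening "Participants will be discontinued from the study if they". The fourth reads "4) develop a serious adverse event (SAE". It carries no condition on cause, arm or clinical need. The third ground, in the same sentence, is limited to medical conditions that rule out use of the iCO monitor.

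Section 8b lists hospitalization among the SAEs, and the list has no causality requirement.

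On what happens after removal, Section 4g says that the person keeps receiving care at the facility and that text messages stop if the exit was due to an adverse event. Section 8b adds safety follow-up: "The participant will be followed and treated by the Investigator until the abnormal parameter or symptom has resolved or stabilized". No section says that a removed participant is still invited to the outcome visits.

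The primary outcome in Section 7c is biochemically verified cessation at 1 month. Table 1 in Section 4b places the CO and urine tests for it at visit 3. Section 7c plans intent-to-treat analyses in which "participants who are lost to follow-up will be considered smokers from the date of last contact". The Sample Size text says that this pilot is not powered for a between-arm comparison but "will provide estimates for future larger studies".

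**The concern.** Stopping an intervention and stopping follow-up are separate decisions. Section 4f merges them. A participant admitted to hospital for a reason unconnected with the study, and discharged well before the 1-month visit, would be removed although a breath test and urine sample could still be taken.

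The safety gain is hard to see. In the brief-advice arm there is no app or monitor to withdraw, and the standardized counseling is given at the initial assessment, before the participant receives the group assignment. Removal there mainly ends measurement, together with any further counseling after a positive test.

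Hospital admissions are not far-fetched in this population: Section 4a recruits partly through inpatient facilities, with screening after discharge.

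At stake are avoidable missing primary outcomes in a trial meant to supply estimates for a larger one. An analysis described as intent-to-treat would then use an assigned status where an observed one could have been had.

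**Working it through.** The plan gives no SAE rate and no dropout allowance, so it has no figure of its own to reproduce. The check has two parts.

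**1. Does the text end outcome collection?**

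- Section 4f: the action is discontinuation from the study, and the SAE ground is unqualified.
- Section 4f, third ground: where the authors wanted a link to the monitor, they wrote one. The SAE ground has none.
- Section 4g: text messages stop after an AE-related exit; outcome visits are not mentioned.
- Section 8b: the participant is followed until the event resolves or stabilizes. This is safety follow-up, with no CO or cotinine test attached.
- Section 4b, Table 1: the primary outcome needs attendance at visit 3.

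The plain reading is that the remaining visits and weekly calls end. This is an inference from the words of 4f and the absence of any provision to the contrary.

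**2. How large could the effect be?**

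Inputs from Section 7c, Sample Size: 150 participants randomized 1:1, so 75 per arm; anticipated cessation 20% and 10%.

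Assumptions, not in the documents:

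- A proportion r has an SAE before the 1-month visit, equal in both arms and unrelated to quitting.
- A share a of these could still have attended.
- Removed participants are counted as smokers.

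Expected quitters with complete follow-up: 75 × 0.20 + 75 × 0.10 = 15 + 7.5 = 22.5.

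Formulas:

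- participants removed = 150 × r
- quitters not observed because of the rule = 22.5 × r × a
- expected difference compared with full attendance = (20 − 10) × (1 − r × a) points

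With a = 1, the upper bound on what the rule costs:

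| Assumed r | Removed | Quitters unobserved | Expected difference | Shift |
|---|---|---|---|---|
| 0 | 0 | 0 | 10.0 | 0 |
| 1% | 1.5 | 0.225 | 9.9 | 0.1 |
| 2% | 3.0 | 0.45 | 9.8 | 0.2 |
| 5% | 7.5 | 1.125 | 9.5 | 0.5 |

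Some SAEs, such as death or a long admission, would prevent attendance whatever 4f says. If only half could have attended (a = 0.5, also assumed), the shift due to the rule at r = 5% is 10 × 0.05 × 0.5 = 0.25 points.

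For scale, the 95% confidence half-width for the difference at 75 per arm is 1.96 × √(0.20 × 0.80/75 + 0.10 × 0.90/75) = 1.96 × 0.0577 = 0.113, or about 11.3 points.

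**The case against.** **No section says that visits stop.** The only operational step in 4g is that text messages end. Section 8b mentions closer monitoring and suspension of treatment as possible responses to an event, which fits a person still under observation. This stands in part: the loss of the outcome is inferred, and a reader should not take it as a stated instruction. But 4f is the text that deals directly with removal. The responses in 8b are examples of what staff should document, and they do not override it.

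**The analysis already copes.** Section 7c commits to intent-to-treat, counts those lost to follow-up as smokers, calls this conservative, and compares losses between arms. This largely stands. Participants removed under the protocol are not named in that rule, but they would probably be handled the same way. A reader might infer that they are dropped from the analysis, or that intent-to-treat is abandoned; the documents do not support that. What remains is that a status is assigned where one could have been measured.

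**Few people are affected.** Section 8a describes minimal risk, and Section 4b gives about 1.5 months in the study. This stands and sets the severity.

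**A separate document may settle it.** Section 8a says: "A safety protocol will be written and closely adhered to for participants who experience serious adverse events". That document may well govern how events are handled and reported. Nothing here says that it restores outcome visits or displaces 4f.

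**Conclusion.** The point holds as a minor one. As written, 4f discontinues from the study any participant in either arm with an SAE of any cause, and no section provides for continued outcome visits. It therefore appears to end 1-month outcome collection for some participants who could still attend, and they would probably be counted as smokers.

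At an assumed SAE rate of 1% to 5%, equal across arms, the expected 10-point difference moves by at most about 0.5 points. That is less than one twentieth of the 11.3-point half-width, and the true effect is smaller if some could not have attended anyway. These figures rest on assumed rates and on the anticipated 20% and 10%.

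Two stronger readings are not supported:

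- A reader might infer that the rule biases the comparison between arms. Unequal removal could move the estimate either way, but the documents give neither an SAE rate nor a reason to expect more SAEs in one arm.
- A reader might infer that safety follow-up ends on removal. Section 8b keeps following the triggering event until it resolves or stabilizes.

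**What to change.** In Section 4f, take the SAE ground out of the list of reasons for leaving the study. State instead that an SAE may stop use of the app or monitor when clinically indicated but does not end study follow-up.

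In Section 4g, add that the planned 2-week and 1-month visits and the weekly calls continue after an SAE unless the participant withdraws consent or cannot attend. Follow-up of the event itself stays as it is.

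The cost is one or two sentences in each section and a few more of the visits and calls already planned. No change to the sample size or the analysis method is needed.

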**5. Inclusion/Exclusion Criteria**

Coach2Quit RCT protocol  
Version: 2.4

Dated: 15 May 2017

Participants are eligible to take part in this trial if they meet the following **inclusion criteria**: (1)  $\geq 18$  years of age; (2) current, daily smokers, (3) agree to participate and anticipate to be living in Baltimore for at least 2 months, (4) own a phone that is compatible with the app, (5) be willing to set at baseline assessment a quit date within 2 weeks.

Participants will be **excluded** if they (1) are suffering from any unstable medical condition *precluding the use of the CO monitor* (e.g. severe COPD); (2) are currently using smokeless tobacco including e-cigarettes; (3) are currently using NRT or other smoking cessation treatment, (4) are pregnant, determined by participant self-report or (5) have a negative baseline result on both urine cotinine AND CO monitor.

## **6. Drugs/ Substances/ Devices**

### **COach2Quit smartphone application and iCO monitor**

Participants assigned to the COach2Quit arm will receive behavioral counseling (described above) and will download the COach2Quit app on their phone. They will be given an individualized carbon monoxide (iCO) monitor and instructed on how to use it with the COach2Quit app. Participants will receive 2 messages daily (1 in the morning and 1 in the evening) requesting them to use the iCO monitor. The iCO monitor has been developed by CoVita™ Bedfont®, and has been made available for the COach2Quit application. The iCO is a personal CO tester that connects to a smartphone via the headphone jack and provides an exhaled carbon monoxide (eCO) reading. Programmers have used the communication protocol supplied by coVita™ Bedfont® to read in data from the iCO monitor and integrate eCO readings with basic feedback messages. The data will be sent to a central data center, with a response message dependent upon CO result. **A measurement of  $\leq 10$  parts per million (ppm) will be a negative result** and will be followed with a message praising the participant's progress. If a positive result is read ( $>10$  ppm), a message of encouragement will follow, along with questions to be answered so that the result can be better understood and acted upon. Subsequent messages will be based on how the user's current CO reading compares to their previous reading. CO trends will be measured over time and the participant will be able to see a graphical display of their CO levels from initiation in to the study. Encouraging responses will also be received when declines in eCO are observed compared to prior results even if above the 10-ppm threshold. Users of the app will also have the option to request a call from a counselor.

### **Carbon Monoxide Breath Test**

When a smoker smokes a cigarette, or any tobacco product, he/she breathes in carbon monoxide, which competes with oxygen to combine with hemoglobin. Hemoglobin has a 200-250 times greater affinity for CO than for oxygen, thus greatly interfering with the necessary binding of oxygen to hemoglobin. Several machines are available to measure the COHb level in the blood of smokers, providing a means of measuring recent exposure to cigarette smoking. For our study, a point of care test for measuring carbon monoxide will be conducted via the piCO Smokerlyzer from OPS Medical, designed specifically for smoking cessation programs and tobacco control programs. Carbon monoxide will be measured in an exhaled breath in parts-per-million (ppm). **A reading of  $\leq 10$  ppm will indicate abstinence.** Participants will be asked about their smoking history since their last visit and on the day of the CO test. If the participant has a positive CO test, they will be further counseled for smoking cessation if enrolled in the clinical trial. If not in the clinical trial, they will be provided with information from the American Lung Association and referred to the Maryland Quit Line. Results will be recorded and labeled with the participant's study ID, and the participant will see their results immediately and the results will be explained to them.

Dated: 15 May 2017

### **Urine Cotinine Test**

When a smoker smokes a cigarette or uses nicotine replacement therapy, his/her urine will have detectable levels of cotinine, a nicotine breakdown product. Cotinine is found in urine from 2 to 4 days after tobacco use, providing a means of measuring recent exposure to cigarette smoking. For our study, a point of care test for measuring cotinine levels will be conducted via SmokeScreen®, a rapid colorimetric assay from GFC Diagnostics Ltd. Cotinine levels will be semi-quantified according to the color chart included with the tests. A color change to red/orange indicates a positive sample, with a darker color indicating greater nicotine intake. If the participant has a positive urine cotinine test, they will be further counseled for smoking cessation if enrolled in the clinical trial. If not in the clinical trial, they will be provided with information from the American Lung Association and referred to the Maryland Quit Line. Results will be recorded and labeled with the participant's study ID, and the participant will see their results immediately and the results will be explained to them.

## **7. Study Statistics**

### **a. Primary outcome variable**

1. Smoking cessation rates at 1-month among participants using the COach2Quit application and participants only receiving anti-smoking advice.

### **b. Secondary outcome variables**

1. Intermediate variables assessed at the end of treatment including; (1) Urges to smoke; (2) Withdrawal symptoms; (3) Reinforcing Smoking Decisional Balance; (4) Smoking Abstinence Self-Efficacy; and, (5) Satisfaction with the program among all participants

### **c. Statistical plan including sample size justification and interim data analysis.**

#### **Data analysis plan**

**Overview** The primary outcome measure for the RCT is proportion of participants with biochemically verified smoking cessation as of 1-month; the primary exposure is study arm, brief-advice only vs. COach2Quit. We will compare proportions of smoking abstinence between study arms at 1-month.

Covariates of interest (e.g. sex, age, race, ethnicity, education, income, smoking history) will be assessed for relationship to prevalence of quitting. These comparisons will utilize the chi-square test for categorical variables and either the Student's t-test or the Wilcoxon signed rank test for continuous variables. Multivariate logistic models will be generated using forwards stepwise model selection, including study arm and all variables with  $p < 0.2$  or odds ratio  $< 0.5$  or  $> 2.0$  at the univariate level, ultimately generating the most parsimonious model.

We will conduct intent-to-treat analyses, providing the purest analysis for an RCT. For these analyses, participants who are lost to follow-up will be considered smokers from the date of last contact. This approach is conservative, as it will likely include participants who have not received either study intervention, but point estimates will be biased towards the null. This approach has been widely adopted in smoking cessation studies. We will compare rates of losses to follow up across the study arms, and look for differences in characteristics of those lost between the arms.

We will analyze number of smoke-free days obtained from questionnaires by comparing the proportions of smoke-free days between arms with a Wilcoxon signed rank test. We will estimate either the absolute difference in proportions, or after a  $\log(\text{days smoke-free}+1/\text{total days of follow up})$  transform if appropriate, with 95% confidence intervals. We will also measure durability of treatment effects using consecutive visits with biochemically verified smoking cessation.

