### **Initial Assessment**

After obtaining informed consent, an initial assessment will be conducted with participants. Participants will be asked to provide a baseline CO breath test and a urine sample to ascertain smoking status. If a candidate is deemed ineligible or chooses not to participate, they will be provided with information from the American Lung Association and referred to the Maryland Quit Line. Eligible participants will complete the baseline questionnaire which will include sociodemographic information, aspects of smoking history (e.g., years, quit attempts, etc), smoking urges, withdrawal symptoms and reinforcing effects of smoking, confidence to quit smoking, reasons to continue to smoke (pros) and barriers to quitting (cons), and perceived vulnerability to smoking-related illnesses, as well as other domains. A certified smoking cessation interventionist (SCI) will deliver standardized smoking cessation counseling using the National Cancer Institute's 5A's model (described below in section e). After brief counseling, all participants will set a quit date within the next 2 weeks and receive their randomized group assignment.

Participants in the COach2Quit arm will be provided with an individualized carbon monoxide (iCO) monitor along with instructions on the use of the monitor and the COach2Quit application. The SCI will help the participant install the COach2Quit app on their phone, guide them through completing an initial CO breath test using their iCO monitor connected to their smartphone, and answer any questions they may have. Participants will be requested to use their iCO monitor at least twice per day and answer a few questions about the amount smoked that day. The participant will be informed that their results will be sent to the study team through the application each time the participant uses their iCO monitor.

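### The primary 1-month comparison prespecifies no use of baseline breath CO or urine cotinine; fixing one baseline term in advance would be a modest, almost free gain in precision

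*Combined protocol and SAP*

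**What the plan says.** Section 7c (Data analysis plan, Overview) defines the endpoint: "The primary outcome measure for the RCT is proportion of participants with biochemically verified smoking cessation as of 1-month". The comparison follows: "We will compare proportions of smoking abstinence between study arms at 1-month". No test, effect measure, confidence interval or covariate is named for it.

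The next paragraph turns to covariates: "Covariates of interest (e.g. sex, age, race, ethnicity, education, income, smoking history) will be assessed for relationship to prevalence of quitting". The list is open and includes smoking history, but names neither biomarker. It continues: "Multivariate logistic models will be generated using forwards stepwise model selection, including study arm and all variables with" a univariate p below 0.2 or an odds ratio below 0.5 or above 2.0. The plan does not say how these models rank against the comparison of proportions.

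The biomarkers are available at no extra effort. Under Initial Assessment (section 4a): "Participants will be asked to provide a baseline CO breath test and a urine sample to ascertain smoking status". Group assignment is received later in the same visit, after counselling and the setting of a quit date; Table 1 agrees. No section describes stratified randomisation.

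The Sample Size text states the purpose of the trial: "our sample size is not powered to find significant differences between arms, but will provide estimates for future larger studies".

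**The concern.** A pilot meant to supply estimates for a larger trial has the 1-month difference, and the precision of that difference, as its main product. If baseline CO or cotinine predicts quitting, an analysis that leaves them out gives up some precision. It also leaves the estimate from this one sample open to whatever imbalance chance has produced. Randomisation is not described as stratified, so the design does not limit that imbalance.

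The planned logistic models do not fill the gap. Whether a baseline biomarker enters depends on a univariate screen and a forward selection run on few events. The result is a conditional odds ratio from a model chosen after seeing the data, not a prespecified adjusted difference in quit rates.

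**Working it through.** **Inputs from the documents.** Anticipated rates: "We anticipate cessation rates of 20% in the COach2Quit arm and 10% in the brief-advice only arm at 1-month". Size: "We will enroll 150 participants into the study over 4 months, randomized 1:1", so 75 per arm. Participants lost to follow-up are counted as smokers, so all 150 are analysed. The plan gives no precision or power figure for the primary difference and no derivation of 150, so there is no plan figure to reproduce.

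**Assumed, because the documents are silent.** A two-sided 95% interval, and the prognostic strength of baseline CO, expressed as an odds ratio (OR) for quitting per SD higher baseline value.

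**Step 1: unadjusted precision.**
SE = √(0.20×0.80/75 + 0.10×0.90/75) = √(0.002133 + 0.001200) = 0.0577.
Half-width = 1.96 × 0.0577 = 0.113, or 11.3 points.

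**Step 2: expected events.** 75×0.20 + 75×0.10 = 22.5 quitters. That supports one or two baseline terms, not a search over many.

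**Step 3: gain from adjustment.** Trials were simulated with 75 per arm and one standard normal baseline covariate. The logistic intercepts were set so that the marginal rates stayed at 20% and 10%. The crude difference was compared with the difference standardised from a logistic model with arm and covariate. Adjusted half-width = 11.3 × √(1 − variance reduction). Ranges show the spread over repeat simulations.

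| OR per SD | Variance reduction | Half-width (points) |
|---|---|---|
| 1.0 | about 0% | 11.3 |
| 0.77 | about 0% | 11.3 |
| 0.67 | about 1% | 11.3 |
| 0.5 | 3% to 5% | 11.1 to 11.0 |
| 0.4 | 7% to 9% | 10.9 to 10.8 |
| 0.33 | 12% to 13% | 10.6 |
| 0.2 | 21% to 23% | 10.1 to 9.9 |

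Both estimators averaged about 0.10 in every scenario, so neither is biased. With no prognostic value (OR 1.0), adjusting cost well under 1% of variance.

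**Step 4: chance imbalance.** The standardised difference in baseline means between arms has SD √(2/75) = 0.163. Its 95% range is ±1.96 × 0.163 = ±0.32 SD, and it exceeds 0.25 SD in either direction with probability 12.6%. A 0.25 SD imbalance moves the crude difference by about 0.8, 1.0, 2.0 and 2.7 points for ORs of 0.77, 0.67, 0.5 and 0.4. The anticipated effect is 10 points.

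**The case against.** The strongest reply is that nothing here is wrong. Under randomisation the crude difference is unbiased, and its interval already allows for chance imbalance. The plan disclaims power, and a half-width of 10.9 instead of 11.3 points would hardly change the planning of a later trial. It also already contains logistic models with study arm and an open covariate list, so CO or cotinine could enter. The gain may be smaller still: cotinine is only semi-quantitative, and candidates negative on both markers are excluded, which narrows the baseline range. All of this stands. What remains is that no baseline term is guaranteed, the ranking of the analyses is unstated, and the improvement costs almost nothing.

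A reader might infer more, in two ways.

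- *That the gain is large.* This borrows a baseline-outcome correlation typical of a continuous measure adjusted for its own earlier value. Here the outcome is binary, every entrant is a current daily smoker, and CO marks intensity of exposure. A gain above 20% of variance needs an OR of about 0.2 per SD, for which the documents give no support.
- *That some entrants already meet the endpoint at baseline.* Section 6 treats a reading of 10 ppm or less as abstinence, and section 5 excludes only those negative on both markers. But the section 4a overview has self-report verified by both CO and cotinine, and any entrant with low CO must be cotinine-positive at baseline. Such a person would pass automatically only if cotinine and self-report were both ignored at 1 month, which the plan does not say. If that did happen, the fault would lie in the endpoint definition, and covariate adjustment would not repair it.

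**Conclusion.** The point holds as a modest improvement to the plan. The primary contrast is crude as written, the two baseline biomarkers are not prespecified for it, and the only adjustment is data-driven on about 22 expected quitters. The pilot's estimate is neither biased nor invalid without the change.

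For ORs between 1.0 and 0.4 per SD, the benefit is about 0% to 7% of variance (9% at the top of the simulated range) and at most about half a point off an 11.3-point half-width. It also removes roughly 1 to 3 points of error in a sample where the baseline happens to be out of balance by 0.25 SD. These figures rest on the plan's 20% and 10% rates, 75 per arm, a two-sided 95% interval, one roughly normal baseline term and an assumed prognostic strength. The last is the decisive unknown.

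**What to change.** In section 7c, before outcomes are examined by arm:

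- Name the primary estimate as a risk difference in verified 1-month cessation, standardised over all randomised participants from a logistic model with study arm and one baseline term, log breath CO in ppm.
- Report it with a robust or bootstrap 95% confidence interval, keeping the existing rule that counts those lost to follow-up as smokers.
- Keep the crude difference in proportions, with its interval, as a sensitivity analysis.
- Label the stepwise logistic models exploratory.

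The cost is one paragraph and a little programming, with no new data, visits or participants. The downside is that little is gained if baseline CO predicts quitting weakly. With so few events, the model should stay at this one baseline term.
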